Public Health
England

NHS
Chelsea and Westminster Hospital
NHS Foundation Trust

PrEP Impact Trial

TRIAL PROTOCOL

Protocol Title:	PrEP Impact Trial: A pragmatic health technology assessment of PrEP and implementation
Short Title:	PrEP Impact Trial
Protocol Number	SSCR104
Version	3.0, 19 Jun 2018
Chief Investigator:	[name]
Sponsor:	Chelsea and Westminster Hospital NHS Foundation Trust

GCP Compliance Statement

This trial will be conducted in compliance with the protocol, the principles that have their origin in the Declaration of Helsinki 2013 and all applicable regulatory requirements

Synopsis

Title:	PrEP Impact Trial: A pragmatic health technology assessment of PrEP and implementation
Short title:	PrEP Impact Trial
Protocol Number:	SSCR104
Trial drug:	Tenofovir Disoproxil (TD)/ Emtricitabine (FTC) The generic product, manufactured by Mylan, is bio-equivalent to the branded product (Truvada) and is provided off label for event-based dosing in accordance with established practice supported by clinical evidence.
Background and rationale:	New prevention efforts are required to reduce the estimated 4,700 incident HIV infections occurring annually in England, of which 2,800 occur among men who have sex with men (MSM). Tenofovir containing regimens used as HIV PrEP are highly effective at reducing HIV acquisition. The data from the PROUD trial in the UK reinforced the evidence for efficacy, though the relatively small sample prevented the results being generalised to all GU clinic attendees and left unanswered key questions about large-scale use of PrEP. The PrEP Impact Trial aims to address these outstanding questions about PrEP, eligibility, uptake and duration of use of PrEP through expanding the assessment to the scale required to obtain sufficient data. In addition the new trial will assess under real world conditions the impact of PrEP on new HIV diagnoses and on sexually transmitted infections, compared to historical controls. The results will inform service commissioners about how to support clinical and cost effective PrEP access in the future.
Aim:	To test the hypothesis that consensus estimates using best available data on PrEP need, uptake and duration of use are correct and, if not, provide accurate measures across the complexity of the population likely to benefit from this medicinal product. This is required to determine the commissioning of future access to PrEP.

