There is little doubt that, when taken correctly, PrEP can significantly reduce the risk of acquiring HIV for an individual. Nonetheless, when delivered at scale to a population, many factors may influence the impact of PrEP. Investigation of each reported HIV seroconversion in those who begin PrEP within the trial will help to assess the extent of PrEP adherence and provide an indication of effectiveness. Another concern about PrEP use is the potential increase in condomless sex with a consequent increase in bacterial STIs, and there is evidence from other countries that this is happening. Participants in PROUD were already at extremely high risk of HIV and other STIs, so extrapolating from these data may be falsely re-assuring. Those accessing PrEP in a large-scale trial may have a lower STI risk prior to taking PrEP and greater

scope for risk compensation when taking PrEP (compared to PROUD participants). However, given HIV and STI incidence has been monitored using GUMCAD in MSM clinic attendee sub-groups for over five years, the population impact of a large-scale PrEP trial on HIV and bacterial STI incidence will be measured both for those taking and not-taking PrEP and stratified by risk markers.

Therefore, this trial aims to address the outstanding questions agreed between Public Health England, NHS England and professional and community stakeholders. For sufficiently robust answers concerning the components of the PrEP continuum of prevention care (% eligible, uptake, duration, etc.) across the heterogeneity of clinics, clinic attendees and eligibility criteria, a trial size of at least 10,000 person years PrEP is required. To mitigate against future geographical inequity in PrEP provision as many clinics as possible should be recruited to the trial. Trial design, methods and data flows should support regular (i.e. quarterly) 'one-to-one' clinical risk assessments to ensure PrEP is delivered 'as part of an active risk reduction intervention including health education and safer sex promotion' [9].

Essential to any future PrEP programme will be the ability to monitor and audit compliance with eligibility criteria and repeated clinical risk assessments. The central role of the GUMCAD information system to the monitoring and evaluation of PrEP has been endorsed by all stakeholders.

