2. TRIAL OBJECTIVES

1. To measure PrEP-eligibility, PrEP-uptake, duration of PrEP-eligibility and duration of PrEP-use (PrEP prevention care continuum) among Genitourinary Medicine (GUM) clinic attendees,
2. To determine whether or not incident HIV infections in trial participants are due to non-adherence or biological failure,
3. To measure change over time in HIV diagnoses and incidence rate in those at high HIV risk,
4. To measure change over time in bacterial STI diagnoses and incidence rate in those at high HIV risk,
5. To measure the PrEP 'prevention care continuum' by clinic throughput and in different regions.

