probability of being in one of the states, the proportions in each state, the average duration in a given state, and transition between the states. A panel-data hazards model will be used to take into account difficulties with analysis such as between clinic variation, and the potential for more than one PrEP prescription per participant. A Gaussian random effect model will be used to enable between clinic variation to be modelled. The analysis will allow for subjects to drop out and re-enter the analysis dependent on eligibility status and will allow for multiple periods of PrEP use over time.

All analyses will include subject level covariates to assess differences between sub-groups. A time to event analysis will be used to estimate HIV incidence and will incorporate a 'cure fraction' model to take into account that the large majority of participants will not reach a HIV infection end-point. A mixed effects interrupted time-series analysis will be used to estimate the difference in the numbers of new HIV diagnoses between the pre-trial and during-trial periods in participating clinics. A time series analysis using conditional risk set model will be used to estimate STI incidence in those receiving PrEP due to the recurrent nature of STIs.

In addition, particular care will be required in the interpretation of the analyses due to the potential for risk spectrum¹ and health-seeking behaviour² biases. An outline of how these biases may be investigated and accounted for in the analyses is provided in the statistical analysis plan.

1. Risk Spectrum bias refers to the phenomenon that different clinics may have a different mix of patients in terms of risk. There may also be a difference in risk within clinics over time. For example, those participants who are enrolled into the trial early may report different levels of risk compared to those who are enrolled later on.

2. Health Seeking Behaviour bias refers to the phenomenon that participants coming forward to clinical services may be at different levels of risk compared to those who do not.

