8.4 Health Economic Analysis

The PrEP Impact trial findings will be used to update existing PHE and University College London (UCL) PrEP economic evaluation model(s) to inform NHS England of the likely cost-effectiveness and budgetary impact of PrEP delivery via GUM clinics in England.

The economic evaluation will bring together findings from this trial, with an aim to provide an updated preliminary report around 25-30 months into the trial, to inform NHS England of the likely cost-effectiveness and budgetary impact of PrEP delivery via GUM clinics in England. This will involve

updating the existing PHE PrEP economic model(s) using trial findings on HIV risk of individuals who took up PrEP, PrEP effectiveness, risk compensation (changes in bacterial STI diagnosis rates), and duration of PrEP use. The timing proposed for the preliminary report is to enable NHS England to consider best available evidence and make recommendations around a potential PrEP policy, potentially allowing for seamless transition from the trial to a programme. A full economic evaluation report will be finalised following conclusion of the trial.

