8.5 Data Recording and Handling

Data relating to patient demographics, , service provision, PrEP eligibility, outcome of PrEP offer, STI/HIV diagnoses and PrEP prescribing will be collected through the national surveillance and monitoring system, the Genitourinary Medicine Activity Dataset (GUMCAD). The GUMCAD is a mandatory national reporting system that collects data on all sexual health attendances, service provision, STI diagnoses and HIV infection from all GUM and other commissioned non-GUM sexual health services. It is an electronic pseudo-anonymised disaggregated patient level dataset that is reported by over 600 services. In order to maintain confidentiality, subjects are identified only by clinic number and clinic subject number.

Trial specific data will be collected through a web-based trial data collection tool (eCRF), maintained by the trial sponsor. This will include a record of the subject ID number, GUMCAD clinic and subject numbers and SOUNDEX code, allowing this minimal PrEP user data to be linked to the GUMCAD and HARS information systems. Linkage will occur monthly in line with GUMCAD reporting schedules.

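### As specified in Section 8.3, the STI analysis does not measure the change in bacterial STI incidence among people at high HIV risk that Objective 4 asks for.

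*Combined protocol and SAP*

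**What the plan says.** Objective 4 (Section 2) reads: "To measure change over time in bacterial STI diagnoses and incidence rate in those at high HIV risk". Three other places bear on its scope:

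- The Synopsis, under background and rationale, says the trial will assess "the impact of PrEP on new HIV diagnoses and on sexually transmitted infections, compared to historical controls".
- Section 1 says "the population impact of a large-scale PrEP trial on HIV and bacterial STI incidence will be measured both for those taking and not-taking PrEP", with stratification by risk markers. It gives as the basis that "HIV and STI incidence has been monitored using GUMCAD in MSM clinic attendee sub-groups for over five years".
- Section 8.4 lists as an economic-model input "risk compensation (changes in bacterial STI diagnosis rates), and duration of PrEP use".

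Section 8.3 presents its analyses as those that address the objectives. For STIs it offers one: "A time series analysis using conditional risk set model will be used to estimate STI incidence in those receiving PrEP", chosen because STIs recur. For HIV the same paragraph sets the time before the trial against the trial itself, in participating clinics: "A mixed effects interrupted time-series analysis will be used to estimate the difference in the numbers of new HIV diagnoses between the pre-trial" (the sentence goes on to name the second period). Section 8.3 also says that all outcomes will be addressed, that subject-level covariates will be included, and that detail, including the handling of risk-spectrum and health-seeking biases, is in the SAP. No separate SAP text was available for this review.

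**The concern.** Objective and method differ in population and in quantity. The objective covers people at high risk whether or not they take PrEP, and asks for a change. The method covers people on PrEP and names no contrast: no earlier period, no comparison group, no term for time or PrEP state. HIV diagnoses have a before-and-during design; STIs have no counterpart.

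Section 1 raises the possibility that condomless sex and bacterial STIs increase on PrEP, and suggests that participants in this trial may have more scope for such change than those in the earlier UK trial. The economic model needs a change in diagnosis rates, with a preliminary report at about 25 to 30 months. An analyst following Section 8.3 alone would not produce that figure. If a contrast were added later, two choices would shape it: a model whose direct output is not a rate, and the more frequent testing that may come with PrEP.

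**Working it through.** The documents give no STI rate, effect size or precision target, so there is no figure to reproduce. The scope comparison is textual. Three illustrations show what follows from it.

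**1. Coverage.** Input: uptake among eligible people of 20% to 60% (Section 8.1). The share outside a PrEP-only analysis is 1 − uptake, that is 80% at 20% uptake and 40% at 60%.

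With equal baseline rates (assumed), the population rate ratio is u × RR(users) + (1 − u) × RR(non-users). Taking RR(users) = 1.20 (assumed):

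| RR in non-users (assumed) | 20% uptake | 60% uptake |
|---|---|---|
| 0.8 | 0.2×1.2 + 0.8×0.8 = 0.88 | 0.6×1.2 + 0.4×0.8 = 1.04 |
| 1.0 | 1.04 | 1.12 |
| 1.2 | 1.20 | 1.20 |

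The result in users does not fix the quantity in Objective 4. At low uptake it does not even fix the direction.

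**2. What the model returns.** This takes the conditional risk-set model to be a Cox model stratified by event order (Prentice-Williams-Peterson). Its direct output is then a hazard ratio among people with the same number of earlier STIs. Section 8.3 plans no comparison, so this shows what would happen if one were added. The simulation used two independent groups of 1,500 followed for 2 years, a true rate ratio of 1.3, total-time scale, and the fifth and later events pooled. There were three runs per setting, so the figures carry visible simulation error. Rates and gamma frailty variances are assumed. Entries are crude rate ratio / model hazard ratio:

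| STIs per year | frailty variance 0 | 1 | 2 |
|---|---|---|---|
| 0.33 | 1.292 / 1.288 | 1.279 / 1.210 | 1.262 / 1.155 |
| 0.6 | 1.274 / 1.270 | 1.233 / 1.146 | 1.349 / 1.183 |
| 1.0 | 1.292 / 1.292 | 1.277 / 1.146 | 1.270 / 1.118 |

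Without differences in underlying risk there is no attenuation. With them, the hazard ratio falls to about 1.12 to 1.21. A gap-time version (n = 6,000, 0.5 STIs per year, follow-up 0.25 to 3 years, frailty variance 1, 15 runs) gave 1.21 for a true 1.30 and 1.33 for a true 1.50.

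**3. Testing frequency.** Section 5.4.3 and Table 1 place STI screens at the 3-monthly visits. With screening interval T (years) and clearance rate μ = 1 / mean carriage, the share of asymptomatic infections detected is (1 − exp(−μT)) / (μT). Prior screening interval and carriage are assumptions.

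- Carriage 3 months (μ = 4): 0.632 at T = 0.25 and 0.245 at T = 1; ratio 2.58.
- Carriage 6 months (μ = 2): 0.787 and 0.432; ratio 1.82.
- Carriage 12 months (μ = 1): 0.885 and 0.632; ratio 1.40.
- If prior screening was 6-monthly, the ratio is 1.46 (carriage 3 months) to 1.12 (12 months).

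These are rises in detection at unchanged incidence, for asymptomatic infections only. If half of infections were symptomatic and always diagnosed (assumed), the annual-to-quarterly ratio for all diagnoses is (0.5 + 0.5×0.632) / (0.5 + 0.5×0.245) = 1.31 at 3 months' carriage and (0.5 + 0.5×0.885) / (0.5 + 0.5×0.632) = 1.15 at 12 months.

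**The case against.** The strongest reply is that Section 8.3 is a summary. It commits to addressing all outcomes and leaves the detail to the SAP; Section 1 commits to STI results on and off PrEP; and GUMCAD "collects data on all sexual health attendances, service provision, STI diagnoses and HIV infection", so the data exist. This stands as far as it goes. A reader might infer that the trial cannot measure change in STI incidence. The documents do not support that; they show a method missing from Section 8.3. The Synopsis and Section 1 state intentions without a method, so they expose the mismatch rather than settle it.

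A reader might also infer that the conditional risk-set model is itself the obstacle. It is not. It can include non-users, calendar time or time-updated PrEP state, and baseline hazards can be recovered from it. Stratification by event order is an interpretation of the term, and attenuation depends on assumed heterogeneity, though the protocol does expect risk to vary between people.

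On testing, the documents do not say that eligible people were screened annually before PrEP. Appendix 2 ties 3-monthly screening of MSM to general MSM guidance, so the contrast may be smaller. The covariates and bias handling deferred to the SAP may cover testing; Section 8.3 does not name it.

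Finally, Section 1 reports that 27% of those at high risk through a bacterial STI in year 1 remained so in year 2. A reader might infer that any before-after comparison would show a spurious fall. Eligibility (Section 3.3) does not require an STI, so that argument does not apply to this trial's population. It is only a reason not to define the comparison group by a recent STI.

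**Conclusion.** The mismatch holds and rests on the text alone: Section 8.3 as written yields no estimate of change in STI incidence for the Objective 4 population, and no before-versus-during change for the economic model. At the protocol's own uptake range, 40% to 80% of eligible people fall outside the stated analysis. Confidence in this is high, subject to the SAP possibly containing the missing analysis.

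The other two points are secondary and conditional. Attenuation of a true 1.3 to about 1.12 to 1.21 needs event-order stratification, frailty variance of 1 to 2 and 0.33 to 1.0 STIs per year. The 1.4- to 2.6-fold detection effect needs annual prior screening and mean carriage of 12 to 3 months, and it is smaller for all diagnoses. They are reasons to specify the added analysis carefully, not evidence that the planned one is invalid for people on PrEP. The trial's main aim of need, uptake and duration is unaffected.

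**What to change.** Add to Section 8.3, or cite the SAP section that already contains:

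1. A pre-trial versus during-trial analysis of bacterial STI diagnosis rates that mirrors the HIV analysis: a mixed-effects interrupted time series, or a negative binomial model, with person-time or attendee denominators. Use a GUMCAD high-risk group defined identically in both periods and not by a recent STI, for example MSM with a negative HIV test at that clinic in the preceding year.
2. Within the trial period, STI rates by time-updated state (on PrEP; eligible but not on PrEP), taken from the PrEP O codes.
3. Results with and without adjustment for number of STI tests, with test positivity alongside. Both are needed because testing is partly a consequence of PrEP visits, so adjustment changes the quantity estimated.
4. The conditional risk-set model kept as a secondary analysis.

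The cost is protocol or SAP wording and analyst time; the plan requires no new data collection. There are limits to state. Eligibility itself is not coded before the O codes existed (Section 8.6), so pre-trial high risk must be a proxy. The example group covers MSM only. GUMCAD numbers do not carry across clinics (Section 5.9), so non-participants who move cannot be followed.

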8.4 Health Economic Analysis

The PrEP Impact trial findings will be used to update existing PHE and University College London (UCL) PrEP economic evaluation model(s) to inform NHS England of the likely cost-effectiveness and budgetary impact of PrEP delivery via GUM clinics in England.

The economic evaluation will bring together findings from this trial, with an aim to provide an updated preliminary report around 25-30 months into the trial, to inform NHS England of the likely cost-effectiveness and budgetary impact of PrEP delivery via GUM clinics in England. This will involve

updating the existing PHE PrEP economic model(s) using trial findings on HIV risk of individuals who took up PrEP, PrEP effectiveness, risk compensation (changes in bacterial STI diagnosis rates), and duration of PrEP use. The timing proposed for the preliminary report is to enable NHS England to consider best available evidence and make recommendations around a potential PrEP policy, potentially allowing for seamless transition from the trial to a programme. A full economic evaluation report will be finalised following conclusion of the trial.

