5.4.1 Baseline/First Trial Prescription Visit

Following enrolment, and a discussion regarding the trial drug and regimen, assessments and procedures should be done in accordance with established practice based on clinical evidence and include:

- A blood specimen for a 4th generation HIV test must be taken on the day a participant starts PrEP, and in those continuing PrEP unless there is a documented negative 4th generation HIV test result that was collected within 4 weeks of enrolment
- A HIV point of care test is advisable if the participant is starting PrEP the same day and has not had a documented negative 4th generation HIV test within the last 4 weeks, Confirmation of Hepatitis B status with testing if there is no record in the clinic notes, and vaccination (course or booster) if indicated according to clinic guidelines,
- Hepatitis C testing according to established practice supported by clinical evidence,
- Renal assessment including a serum creatinine in all participants that are starting PrEP, and existing PrEP users who have not had a check in the preceding year or require more frequent monitoring (see section 4.7.3),
- STI screen for chlamydia, gonorrhoea and syphilis if indicated according to clinical guidelines and commissioned activity,
- Assessment of pregnancy risk and pregnancy testing, if required - confirmed pregnancy is not a contraindication to PrEP (see section 5.6),
- Prescribing and dispensing of drug according to local practice (see section 5.5) and sufficient to last until the next planned visit,
- Completion of GUMCAD codes within the patient record.

Once assessments have been undertaken, trial drug can be prescribed and dispensed. A record of dispensing should be made in the trial drug log/eCRF.

In line with national guidance, participants will be offered the relevant interventions from an active risk reduction intervention package to reduce and modify high risk behaviour. This may include the provision of free condoms, clean needles, behaviour change interventions, other biomedical interventions such as post-exposure prophylaxis where relevant, the diagnosis and treatment of STIs and a repeat HIV test within 4 weeks to close the window period on a particular risk.

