5.4.2 Early Follow-up in New Starters

For participants who have not taken PrEP or PEP previously, it is good practice to check how the participant is getting on. This can be done by phone email or in person if a visit is indicated for other reasons.

5.4.3 3-monthly Follow-up

In line with established practice, 3-monthly follow up is advised. Standard assessments and procedures at this time should be done in accordance with established clinical practice based on clinical evidence and include:

- A 4th generation HIV test,
- STI screen for chlamydia, gonorrhoea and syphilis according to established practice supported by clinical evidence or if clinically indicated,
- Hepatitis C testing according to established practice supported by clinical evidence,
- Urinalysis and serum creatinine or urinary protein/creatinine ratio if indicated
- Pregnancy testing if indicated clinically (see section 5.6),
- Prescribing and dispensing of drug according to agreed local practice (see section 5.5),
- Completion of GUMCAD codes,
- MHRA Yellow card reporting if appropriate.

The clinician should check that the participant is still eligible for PrEP and wishes to continue, and should record this information using the GUMCAD codes. Once standard assessments have

been undertaken, study drug can be prescribed and dispensed. A record of dispensing should be made in the study drug log/eCRF.

Participants should be offered relevant interventions from active risk reduction services as per the First Prescription visit (Section 5.4.1).

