5.4.4 Annual Follow-up

After each year on PrEP, the following procedures and assessments are advised:

- A 4th generation HIV test,
- STI screen for chlamydia, gonorrhoea and syphilis according to established practice supported by clinical evidence or if clinically indicated,
- Hepatitis C testing according to established practice supported by clinical evidence,
- Serum creatinine,
- Pregnancy testing if indicated clinically (see section 5.6),
- Prescribing and dispensing of drug according to agreed local practice (see section 5.5),
- Completion of GUMCAD codes,
- MHRA Yellow card reporting if appropriate.

The clinician should check that the participant is still eligible for PrEP, and should record this information using the GUMCAD codes. Once standard assessments have been undertaken, trial drug can be prescribed and dispensed. A record of dispensing should be made in the trial drug log/eCRF.

Participants should be offered relevant interventions from active risk reduction services as per the First Prescription visit (Section 5.4.1).

Table 1: Standard Assessments and Trial Procedures

	Recruitment/ Baseline	3-monthly	Annually
Trial procedures			
Inclusion/exclusion criteria	x ^a		
Informed consent	x		
Enrolment on trial database	x		
Record of drug dispensing	x	x	x
Standard assessments and procedures (as part of routine clinical care)			
HIV 4th Generation test	x ^b	x	x
HIV point of care test	x ^b		
Hepatitis B status confirmation (+/- testing and vaccination)	x ^c		
Hepatitis C testing	x ^d	x ^d	x ^d
Renal (Serum Creatinine to estimate creatinine clearance)	x ^e	x ^e	x
Urinalysis	x	x	
STI screen (Chlamydia, Gonorrhoea, Syphilis)	x	x	x
Assessment of pregnancy risk	x ^f	x ^f	x ^f
Prescribing and dispensing of drug	x	x	x
GUMCAD O codes assigned and entered	x	x	x
Yellow card check		x	x

(a) Eligibility will be determined on the basis of information routinely collected in clinic and during the informed consent process,

(b) If a 4th generation HIV test has been done within 4 weeks of baseline then a Point Of Care Test is not required,

(c) Hepatitis B status confirmation +/- vaccination according to national guidance,

(d) Hepatitis C testing according to established practice (which will differ between at risk populations) based on clinical evidence

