8.2 Trial Outcomes

1. Proportion of Genitourinary Medicine (GUM) clinic attendees that meet PrEP eligibility criteria, the proportion that is prescribed PrEP per year and the duration of PrEP-eligibility and PrEP-use among users.

2. HIV and STIs:
 - a. HIV diagnoses in national dataset
 - b. STI diagnoses (gonorrhoea, chlamydia, syphilis and Hepatitis C) in national dataset
3. Adverse Events
 - a. Serious suspected adverse drug reactions reported using the yellow card system
 - b. Antiretroviral resistance associated mutations in participants with incident HIV infection

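### Risk compensation is read from the change in bacterial STI diagnosis rate, which can rise through more frequent screening alone, and the protocol states no adjustment for testing frequency

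*Combined protocol and SAP*

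**What the plan says.** Section 8.4 lists four trial findings that will update the economic model: HIV risk in those taking up PrEP, effectiveness, "risk compensation (changes in bacterial STI diagnosis rates"), and duration of use. A preliminary report is due at about 25 to 30 months to inform NHS England.

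The STI outcome in section 8.2 is "STI diagnoses (gonorrhoea, chlamydia, syphilis and Hepatitis C) in national dataset". The synopsis says the trial will assess the "impact of PrEP on new HIV diagnoses and on sexually transmitted infections, compared to historical controls". Section 1 adds a comparison of people taking and not taking PrEP, stratified by risk markers.

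On testing, the text is as follows.

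- Section 5.4.3: "In line with established practice, 3-monthly follow up is advised". The list for that visit includes "STI screen for chlamydia, gonorrhoea and syphilis according to established practice supported by clinical evidence or if clinically indicated".
- Section 5.4.1, at baseline: "STI screen for chlamydia, gonorrhoea and syphilis if indicated according to clinical guidelines and commissioned activity".
- Table 1 marks "STI screen (Chlamydia, Gonorrhoea, Syphilis") at baseline, 3-monthly and annually, with no footnote, under the block "Standard assessments and procedures (as part of routine clinical care").
- Appendix 2 recommends the screen every 3 months for MSM on PrEP, and as appropriate for heterosexuals.
- Section 5.5 limits supply to 3 months per visit.
- Section 3.3 requires, for population A, a negative HIV test at an earlier episode in the preceding year. It sets no STI screening frequency.

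Section 8.3 models STI incidence in those receiving PrEP with a conditional risk set model, chosen because STIs recur. It names two biases, risk spectrum and health-seeking behaviour, and refers their handling to the SAP.

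**The concern.** Starting PrEP can change two things at once: behaviour, which the economic model wants to capture, and the frequency with which symptom-free infection is looked for. A diagnosis rate responds to both, and nothing in sections 8.2 to 8.4 separates them.

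The parts of the plan that might help do not reach this problem. The conditional risk set model deals with repeat events and names no term for tests. Both biases in section 8.3 are defined by level of risk, not by intensity of testing. The comparison of takers with non-takers keeps the asymmetry, because the takers are the ones on the 3-monthly schedule.

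A related problem arises at the start of PrEP. Where the baseline screen is not done, infections already present are found at the first follow-up screen and counted as arising on PrEP. Section 5.4.1 makes that screen conditional; Table 1 does not.

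Section 1 names an increase in condomless sex and bacterial STIs as a concern about PrEP. If a rise due to testing is read as behaviour, it enters the cost-effectiveness estimate given to the commissioner. The trial is large enough for such a rise to look statistically secure.

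**Working it through.** The plan gives no figure for STI rate change or testing frequency, so there is nothing to reproduce. What follows is an illustration with true incidence held constant.

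**Inputs**

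- Screening interval on PrEP: 3 months (section 5.4.3, advised).
- Screening interval before PrEP: not in the documents; 12, 6 and 3 months are tried.
- Mean duration D of an untreated asymptomatic infection: assumed 3, 6 or 12 months.
- Share a of infections that are asymptomatic: assumed 50% or 80%. Symptomatic infections are assumed always diagnosed.

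**1. Share of asymptomatic infections found.** With infections arising evenly over an interval T and clearing exponentially with mean D, the share still present at the screen is p(T) = (D/T)(1 − exp(−T/D)).

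| D | p, T = 12 months | p, T = 6 months | p, T = 3 months |
|---|---|---|---|
| 3 months | 0.245 | 0.432 | 0.632 |
| 6 months | 0.432 | 0.632 | 0.787 |
| 12 months | 0.632 | 0.787 | 0.885 |

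**2. Apparent rate ratio.** Ratio = [(1 − a) + a·p(3 months)] / [(1 − a) + a·p(earlier T)].

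| D | a | from 12-monthly | from 6-monthly | already 3-monthly |
|---|---|---|---|---|
| 3 months | 0.8 | 0.706/0.396 = 1.78 | 0.706/0.546 = 1.29 | 1.00 |
| 3 months | 0.5 | 1.31 | 1.14 | 1.00 |
| 6 months | 0.8 | 1.52 | 1.18 | 1.00 |
| 6 months | 0.5 | 1.25 | 1.09 | 1.00 |
| 12 months | 0.8 | 1.29 | 1.09 | 1.00 |
| 12 months | 0.5 | 0.942/0.816 = 1.15 | 0.942/0.893 = 1.05 | 1.00 |

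If as few as 20% of infections depend on screening to be found, the lower ends fall to 1.05 (from 12-monthly) and 1.02 (from 6-monthly).

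**3. Would such a rise look real?** Section 1 gives 33% of attendees with a bacterial STI. Read as the yearly chance of at least one diagnosis at a constant rate, this is −ln(1 − 0.33) = 0.40 per person-year. With 10,000 person-years in each period (section 1 asks for at least that much PrEP time), there are about 4,005 events per period. The ratio detectable with 80% power at two-sided 5% is exp[(1.96 + 0.84)·√(2/4,005)] = 1.065. This ignores clustering and repeat infections, so the real figure is larger, but most of the table lies above it.

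**4. Positivity under the same model.** Positives per asymptomatic screen are proportional to T·p(T) = D(1 − exp(−T/D)). Going from 12-monthly to 3-monthly screening with flat incidence changes this from 0.245 to 0.158 (D = 3 months, a fall of 36%), from 0.432 to 0.197 (D = 6 months, 54%), or from 0.632 to 0.221 (D = 12 months, 65%).

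**5. Skipped baseline screen.** If the last screen was 12 months before enrolment and none is done at baseline, the first follow-up screen closes a 15-month gap. The yield relative to later 3-monthly screens is (1 − exp(−15/D)) / (1 − exp(−3/D)), with D in months: 1.6, 2.3 and 3.2 for D = 3, 6 and 12.

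**The case against.** The strongest reply is that the artefact needs screening to become more frequent than it was, and the documents do not show that it does. Table 1 classes the screen as routine care. Section 5.4.3 advises the visit and qualifies the screen. Appendix 2 ties the 3-monthly screen to existing guidance for MSM. Section 5.4.1 expects some people already on PrEP to enrol. The 12-month comparator is suggested only by an HIV-test entry criterion, which is a minimum. All of this stands, so a reader who inferred that the rate must rise would go too far. Other forces may lower it: section 1 reports that only 27% of those at high risk by a bacterial STI in year 1 remained so in year 2, so regression to the mean could work the other way. That is a further uncorrected influence and not a remedy.

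A reader might also infer that positivity should replace the diagnosis rate. Step 4 rules this out: more frequent screening lowers positivity with flat incidence, which could hide real risk compensation.

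A reader might put the first-screen excess as high as 4.5-fold. That figure (1/(1 − exp(−3/12)), D = 12 months) supposes no screening before PrEP and does not fit a 12-monthly history. How often the baseline screen is skipped is also unknown.

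Finally, section 8.3 sends bias handling to a separate SAP that was not available, so an adjustment there cannot be excluded. If one exists, section 8.4 should point to it.

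**Conclusion.** The concern holds as a risk of bias, not as a predicted rise. The protocol takes a diagnosis rate as its measure of risk compensation, advises a visit schedule that may change testing frequency when PrEP starts, and states no adjustment. The size depends on unknown earlier screening: about 15% to 78% from 12-monthly, 5% to 29% from 6-monthly, nil from quarterly. These figures rest on the assumed duration, the assumed asymptomatic share and constant incidence, none of which comes from the documents.

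This should be fixed. It does not affect eligibility, uptake or duration, which are listed first in section 8.2, and the raw rate remains a legitimate input for service load and budget. But as written, a measured rise could not be attributed to behaviour.

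**What to change.** In sections 8.3 and 8.4 (and the SAP), state that the raw change in diagnosis rate will not by itself be read as risk compensation. Report, identically for the comparison period and for time on PrEP:

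1. the raw diagnosis rate, kept as the service-load and budget input;
2. the rate adjusted for or stratified by screening frequency (screens per person-year, or interval since last screen);
3. test positivity, as a companion measure only, with a note that it falls when screening becomes more frequent.

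Carry the range across these into the economic model as a sensitivity analysis.

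Report positives at the first screen at or after enrolment separately, as possibly prevalent, and start on-PrEP STI time from that screen. Reconcile the baseline STI screen between section 5.4.1, where it is conditional, and Table 1, where it is not.

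The cost is some extra analysis and a few early events set aside. Section 8.5 says GUMCAD records attendances and service provision, but not whether individual tests are coded. That must be confirmed; if they are not, attendance frequency is the fallback for the adjustment.
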